6.5. Pooling of Centers

There are approximately 25 investigative sites participating in the study. It is likely that the number of subjects recruited by each site will be small. The primary analysis will use data pooled across sites. No descriptive summaries by site are planned.

6.6. Subgroups

Randomization was stratified by asthma comorbidity. Hence, statistical analysis will explore treatment differences for the co-primary endpoints in subgroups defined by asthma comorbidity. Specifically, treatment effects will be explored in subjects with and without comorbid asthma.

Among the exploratory efficacy endpoints, changes from baseline in FEV1 and percent predicted FEV1 will be analyzed for asthma subgroup in addition to the overall group, and the ACQ-7 will be analyzed in the asthma subgroup only.

Additional subgroup analyses such as by weight may be performed post-hoc, as needed.

7. DEMOGRAPHIC, OTHER BASELINE CHARACTERISTICS AND MEDICATION

7.1. Subject Disposition and Withdrawals

A summary of subject disposition will be provided including the number of subjects screened, number of screen failures, number randomized, number treated, completed the study as well as the number of subjects who discontinued early from the study. Reasons for early discontinuation from the study will be summarized.

For subjects enrolled but screen failed, the denominator used to calculate the percentage will be the number of enrolled subjects (subjects who have signed the informed concent form). For all other calculations, the denominator will be the number of subjects randomized. Subject disposition will be presented overall and by treatment group.

The number of subjects in each analysis set (Enrolled, FAS, Safety, PP, PK) will also be summarized.

A separate summary will be provided of the number and percentage of subjects attending each visit. Percentages will be based on the FAS. A listing of subject visits will be provided for all subjects.

7.2. Inclusion/Exclusion Criteria

Inclusion/exclusion criteria definitions and violations will be listed for all enrolled subjects. If no inclusion/exclusion violations are reported, this will be noted in place of the listing.

7.3. Protocol Deviations

A protocol deviation is any noncompliance with the clinical trial protocol, ICH GCP, or MOP requirements. The noncompliance may be either on the part of the subject, the investigator, or the study site staff.

In addition to site level deviations, individual subject level protocol deviations may include (but are not limited to) the following. Details of each deviation are specified in the Protocol Deviation and Non-compliance Management Plan.

- Concomitant Medication
- Enrollment Criteria
- Informed Consent
- Dosing
- Non-Compliance
- Regulatory
- Visit Schedule
- Visit/Procedure Required
- Other
- Laboratory

Multiple deviations can occur in the same subject and thus a subject can be counted in more than 1 deviation category.

Deviations may be categorized as major or minor. Major deviations will be summarized in a table for Enrolled set. All deviations (major or minor) will be presented in a subject listing sorted by treatment and summarized for Enrolled set.

Major protocol deviations that are thought to affect the evaluation of efficacy and/or safety will lead to exclusion of subjects from the PP Analysis Set. This determination will be made by the sponsor after joint review of all major protocol deviations by the study team prior to unblinding.

7.4. Demographic and Other Baseline Characteristics

The following demographic characteristics will be summarized for the FAS and Safety analysis Sets:

- Age [Years]
- Age category ($< 65, \ge 65$ years)
- Sex
- Race
- Ethnicity
- Height [cm]
- Weight [kg]
- BMI [kg/m²]
- Asthma comorbidity (yes/no)
- Smoking status (never, current, former), Number of cigarettes packs smoked per day
- Child-bearing potential

In case age is not provided in the CRF and needs to be calculated, it will be calculated as:

```
Age (at Screening = (Informed consent date - date of birth + 1) / 365.25 and truncated to complete years.
```

- Weight will be converted to kilograms (kg) when reported in pounds (lbs) as follows: Weight (in kg) = weight (in lbs) * 0.4536
- Height will be converted to centimeters (cm) when reported in inches (in) as follows: Height (in cm) = height (in inches) * 2.54/100

All subject demographics data will be listed for the Enrolled Set.

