- Incidence of adverse events (AEs) and treatment-emergent AEs (TEAEs)
- Incidence of serious adverse events (SAEs)
- Changes in clinical laboratory tests (hematology, chemistry, and urinalysis)
- Changes in vital signs (blood pressure [BP], temperature, respiration rate, and pulse rate)
- Changes in electrocardiogram (ECG) parameters
- Immunogenicity (anti-drug antibody [ADA] and neutralizing ADA)
- Apparent clearance (CL/F)
- Apparent volume of distribution
- Maximum concentration (Cmax)
- Time of maximum concentration (t_{max})
- Area under the concentration-time curve from time 0 to the time of the last quantifiable concentration (AUC_{tau})
- Apparent terminal half-life $(t_{1/2})$ will also be determined for etokimab after SC administrations, as possible

Study Population:

Approximately 100 adults between the ages of 18 and 70 years of age with CRSwNP with a minimum bilateral Nasal Polyp Score of 4 out of 8 (maximum score) (with minimum score of 1 in each nostril) despite completion of a prior INCS treatment for at least 8 weeks before Screening. Presence of at least 2 of the following symptoms prior to Screening: nasal blockade/obstruction, nasal congestion, or nasal discharge (anterior/posterior nasal drip), facial pain/pressure, and/or reduction in or loss of smell.

Phase:

Description of
Sites/Facilities Enrolling
Participants:

Approximately 25 investigative sites across the United States (US) are expected to participate in this study.

Approximately 100 subjects will be enrolled (approximately 33 evaluable subjects per treatment arm).

Description of Study Intervention:

Etokimab or matching placebo for SC injection:

- Sterile etokimab in single-use glass vials; each vial will contain 100 mg/mL of etokimab.
- Sterile placebo in identically matched single-use glass vials; each vial will contain no active drug product.

See Figure 1 for dosing regimen.

Study Duration: Study duration will last approximately 12 months.

[figure not shown]
Participant Duration: Participant duration includes:

- 4-week screening period (maximum of 31 days) with a minimum MFNS run-in period of 20 days
- 16-week treatment period
- 8-week follow-up

The total participant duration is expected to be up to 28 weeks.

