3.5.1. Inclusion Criteria

Subjects must meet all of the following criteria in order to be eligible to participate in this study:

- 1. Male or female, aged 18 to 70 years at the time of consent.
- 2. Present with a minimum bilateral total nasal polyp score of 4 out of 8 (maximum score), with minimum of 1 in each nostril, despite completion of a prior intranasal corticosteroid (INCS) treatment for at least 8 weeks before screening.
- 3. Present with at least 2 of the following symptoms prior to screening:
 - a. Nasal blockade/obstruction
 - b. Nasal congestion
 - c. Nasal discharge (anterior/posterior nasal drip)
 - d. Facial pain/pressure, and
 - e. Reduction in or loss of smell.
- 4. Body mass index (BMI) of 18 to 42 kg/m² (inclusive) and total body weight > 50 kg (110 lb).
- 5. Agrees to the following conditions regarding contraception and pregnancy:
 - a. A male subject must agree to use contraception as detailed in the protocol during the treatment period and for at least 3 months after the last dose of study treatment and refrain from donating sperm during this period.
 - b. A female subject of child bearing potential must have a negative serum pregnancy test (β -human chorionic gonadotropin) at screening and a negative urine pregnancy test at baseline (Day 1), is not lactating, and at least one of the following conditions applies:
 - i. Not a woman of childbearing potential (WOCBP) as defined in the protocol OR
 - ii. A WOCBP who agrees to follow the contraceptive guidance in the protocol during the treatment period and for at least 3 months after receiving the last dose of study treatment. The female subject's selected form of contraception must be effective by the time the female subject enters into the study (e.g., hormonal contraception should be initiated at least 28 days before Study Day 1).
- 6. Screening laboratory values must meet the following criteria:
 - a. AST and ALT levels $\leq 3 \times ULN$
 - b. Total Bilirubin $\leq 1.5 \text{ x ULN}$

c. Albumin \ge 3 g/dL - Lipase \le 1.5 ULN (if collected)

If a subject has liver function tests (LFTs) within normal and defined limits at screening and meets all other inclusion criteria at screening and baseline, the subject can be dosed.

- 7. Capable of giving signed informed consent and understanding the requirements and restrictions listed in the informed consent form (ICF).

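### SAP 7.4 converts inches with a factor that returns metres under a centimetre label, so the height of any subject recorded in inches would be reported 100-fold too small

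*SAP*

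**What the plan says.** SAP 7.4 lists height in cm and BMI in kg/m² among the characteristics to be summarised for the Full Analysis Set and the Safety Analysis Set, and has all demographic data listed for the Enrolled Set. It then gives unit conversions. For height the introduction reads "Height will be converted to centimeters (cm) when reported in inches (in) as follows" and the rule is "Height (in cm) = height (in inches) * 2.54/100". The companion rule for weight is "Weight (in kg) = weight (in lbs) * 0.4536".

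The section gives no formula for BMI. It does not say whether BMI is derived by the programmer or taken from the eCRF. No other section of the SAP or protocol restates or corrects the height conversion.

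**The concern.** The rule contradicts itself: its left-hand side, its introduction and the summary unit are all centimetres, but the arithmetic on the right gives metres. This is an operative derivation rule, so a programmer must either apply it and produce wrong heights, or depart from the SAP without a documented reason.

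At stake is the baseline height row and listing, and possibly BMI. The rule applies only to heights reported in inches. If some heights are recorded in inches and others in cm, the converted column would therefore hold two different units under one label.

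**Working it through.** **Inputs from the documents**
- Height factor as written: 2.54/100 (SAP 7.4).
- Stated output unit: cm (SAP 7.4).
- Weight factor: 0.4536 kg per lb (SAP 7.4).
- Plausible BMI range, from the inclusion criterion: "Body mass index (BMI) of 18 to 42 kg/m² (inclusive) and total body weight > 50 kg (110 lb") (SAP 3.5.1).

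**Illustrative inputs (assumptions, not in the documents)**
- Heights of 60, 67 and 74 in; a weight of 180 lb; one further subject recorded as 170 cm.

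**Step 1. The factor.** 2.54/100 = 0.0254, which is metres per inch. Centimetres per inch is 2.54. The ratio is 2.54 / 0.0254 = 100.

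**Step 2. Effect on height.**

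| Recorded (in) | SAP rule, labelled cm | True cm |
|---|---|---|
| 60 | 60 × 0.0254 = 1.524 | 60 × 2.54 = 152.40 |
| 67 | 67 × 0.0254 = 1.7018 | 67 × 2.54 = 170.18 |
| 74 | 74 × 0.0254 = 1.8796 | 74 × 2.54 = 187.96 |

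**Step 3. Effect on a mixed column.** Take one subject recorded as 170 cm and one as 67 in. Under the rule the mean is (170 + 1.7018)/2 = 85.85. The true mean is (170 + 170.18)/2 = 170.09.

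**Step 4. Effect on BMI.** The SAP gives no formula, so both possible uses of the converted value are shown for 67 in and 180 lb. The weight is 180 × 0.4536 = 81.65 kg.
- True value: 81.65 / 1.7018² = 28.19 kg/m².
- Label followed, so the value is treated as cm and divided by 100 again: 81.65 / (1.7018/100)² = about 281,922 kg/m². This is 100² = 10,000 times too large.
- Value used directly as metres: 81.65 / 1.7018² = 28.19 kg/m², which is correct.
- The formula that works in the previous line fails for a cm-recorded subject. With 170 cm and an assumed 80 kg, 80 / 170² = 0.0028 kg/m².

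No single BMI formula applied to the height variable is therefore right for both kinds of subject.

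**Step 5. The companion rule.** 110 lb × 0.4536 = 49.9 kg, which agrees with the 50 kg (110 lb) limit in the inclusion criterion. The weight conversion is sound, so the error is confined to height.

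**The case against.** The strongest case on the other side accepts the slip and disputes its reach. Most of that case stands.

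- **BMI.** A reader might infer that every BMI derived from a converted height is wrong. The documents do not support that. BMI needs metres, which is what the rule returns, and the SAP does not say how BMI is obtained. It is wrong for inch-recorded subjects only if computed from the value as labelled.
- **Eligibility.** Because BMI of 18 to 42 kg/m² is an inclusion criterion, a reader might infer that the error could admit or exclude subjects. Height is measured at Screening (protocol 1.3) and eligibility is settled before randomization, whereas SAP 7.4 governs summaries and listings. Nothing shows that sites use this conversion, and SAP 7.2, which lists eligibility violations, does not say that they are recomputed from it.
- **Efficacy.** Height and BMI do not appear in the co-primary models (SAP 8.1), the secondary analyses (SAP 8.2) or the sample size (SAP 3.6). The possible post-hoc subgroup in SAP 6.6 is by weight, whose conversion is sound. Percent-predicted FEV₁ uses reference equations set on the spirometer (protocol 8.1.8.6), not this rule.
- **Frequency.** The rule acts only on heights reported in inches, and the documents do not say whether there are any. The protocol synopsis states: "Approximately 25 investigative sites across the United States (US) are expected to participate in this study". That makes inches plausible but does not establish them. If every height is recorded in cm, the effect is nil.
- **Visibility.** A height of 1.70 cm would be conspicuous in any table or listing.

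These points limit the severity. They do not make the formula correct.

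**Conclusion.** Wrong as written, low severity. The conversion returns metres under a centimetre label, so reported height would be exactly 100-fold too small for each inch-recorded subject. This part needs no assumption beyond 1 inch = 2.54 cm.

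The 10,000-fold BMI error is conditional: it requires that BMI is derived in programming and that the converted value is taken at its label. The total effect on the summaries depends on the number of inch-recorded heights, which is unknown. The reach is the descriptive demographic summaries and listings. No eligibility decision, efficacy result or power figure is shown to depend on the rule.

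**What to change.** In SAP 7.4, delete the division by 100, so that height_cm = 2.54 × height_in. In the same section, state whether BMI is taken from the eCRF or derived. If derived, define it as weight in kg / (height in cm / 100)², which then holds for all subjects whatever unit was recorded.

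The cost is a short text correction and a matching check of the derivation program. Design, data collection and efficacy analyses are unchanged.

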7.5. Medical History

Medical history information will be coded using the Medical Dictionary for Regulatory Activities (MedDRA) version 21.0 or higher, summarized and presented overall and by treatment group for the Safety Analysis Set. Summaries will be ordered alphabetically by system organ class (SOC) and then, within a SOC, alphabetically by preferred term (PT).

The number and percentage of subjects will be displayed for each System Organ Class and Preferred Term within treatment group.

A listing of medical history will be presented for the Safety Analysis Set.

7.6. Prior and Concomitant Medication

Prior and concomitant medications will be coded using World Health Organization Drug Dictionary (WHO-DD) March 2018 or later.

Prior medications are defined as any medication that was stopped prior to the first dose of study medication. Concomitant medications are defined as any medication that is ongoing at the time of the first dose of study medication or is started after the first dose of study medication.

Prior and concomitant medications will be separately summarized by presenting the counts and percentage of subjects with medications/therapies overall and by each treatment group for the Safety Analysis Set. Medications will be summarized and sorted alphabetically by Anatomical Therapeutic Chemical (ATC) categories (ATC level 2 categories) and then by the preferred name within the ATC level 2 category. Subjects will be counted only once for each medication class and each preferred drug name.

Prior and concomitant medications/therapies will be listed together with a designation to identify the medications/procedure as prior and/or concomitant and sorted by start date.

8. EFFICACY

The primary efficacy objective of this study is a comparison of each of two dosing regimens of etokimab with placebo in the treatment of subjects with CRSwNP following a 16-week treatment period (change from baseline using co-primary endpoints). Two co-primary efficacy endpoints will be analyzed.

The analysis of the primary and secondary efficacy parameters will be performed on the FAS, unless otherwise noted. The primary and secondary efficacy analyses will be repeated on the PP analysis set if there are substantial differences between the makeup of the FAS and the PP Analysis Set, in order to assess the impact of major protocol deviations on the key inference.

All primary and secondary efficacy variables will be analyzed for data obtained for the Treatment Period.

8.1. Primary Efficacy Endpoint and Analysis

Statistical hypotheses associated with the co-primary efficacy endpoints are as follows:

- Treatment of adults diagnosed with CRSwNP using etokimab will result in a significantly greater reduction of Week 16 NPS from baseline when compared to placebo, and
- Treatment of adults diagnosed with CRSwNP using etokimab will result in a significantly greater reduction of Week 16 SNOT-22 score from baseline when compared to placebo

Statistical significance for the co-primary efficacy endpoints will be declared if and only if both 2-sided pvalues for the tests of the individual hypotheses are < 0.05. Testing will be conducted in a hierarchical manner for each co-primary endpoint such that the comparison of the etokimab Q4W treatment arm versus placebo will be conducted first. If the result from this test is statistically significant, then the comparison of the etokimab Q8W treatment arm versus placebo will be performed. If the result from the etokimab Q4W versus placebo is not statistically significant, no further testing will be performed for the etokimab Q8W treatment arm versus placebo.

8.1.1. Nasal Endoscopy

Nasal endoscopy is performed acc ording to the schedule of assessments in Table 1, on Day 1, Week 4, Week 8, Week 12, Week 16 and Week 24. Each nostril is scored on a scale of 0 to 4, and hence the total NPS value at each visit is between 0 and 8. For each nostril, a score of 0 means no polyps, while a score of 4 means the presence of polyps causing complete obstruction of the inferior nasal cavity. The NPS value at the screening visit is used to determine qualification for enrollment in the study. The NPS score at Week 24 is for safety follow-up.

If a subject's NPS image is initially evaluated as unreadable, the subject may be asked for a repeat endoscopy. If the original image is taken during the screening period, the subject will be asked to repeat endoscopy. If the original image is during post-randomization, the endoscopy will not be repeated with the exception of the Week 8 and Week 16 images. If the images taken for the Week 8 or Week 16 visits are not readable, every attempt should be made to repeat the procedure as close to the original visit window and the re-taken image will be used for analysis. For analysis purposes, baseline endoscopic score (NPS value) will be defined as the total (left and right) NPS value reported at the last visit on or prior to the first dose date (Day 1). Total NPS values will also

be obtained at each visit during Treatment Period (Week 4, 8, 12 and 16), and at the end of the Safety Followup Period (Week 24).

A listing of nasal endoscopy performance, nasal polyp scores, and change from baseline scores will be provided per visit per subject for the Full Analysis set.

8.1.1.1. Definition of Estimand

Subjects who permanently stopped the study medication are not required to withdraw from the study. Subjects were informed that if they decided to discontinue study medication, they had the option of providing clinic assessments at scheduled office visits or by phone contact until the planned end of their study visits.

Thus, the (co)primary estimand chosen here is the de facto or treatment policy estimand, which uses the available on-treatment NPS values during Treatment period. The primary time point is Week 16.

The NPS is also measured every 4 weeks during treatment and at end of treatment (Week 16). A general linear mixed model with repeated measures (MMRM) will be used to obtain least squares means of change in NPS at Week 16 from baseline, to compare the etokimab treatment arms with the placebo arm.

Summary statistics for each time point will include n, mean, standard deviation, median, minimum, and maximum, for baseline, each time of measurement, and the change from baseline calculated as post-baseline value minus the baseline value.

